card will be erased. At the end of the night the camera and memory card will be stored in a locked cabinet. The recordings will be stored on the server until all recordings have been transcribed, at which point they will be deleted. No publications or presentations resulting from this research program will contain any identifying information about individual participants. Conduct of study events for EMA reporting, data collection, and tracking of progress is guided by a customized database as we have used previously developed with the assistance of the UW DoIT team. Data are entered into Qualtrics™, a computerized assessment resource with built-in quality assurance and security features (e.g., not permitting skipped or out-of-range values). Data are stored securely and accessed in accord with all UW, state, and federal regulations.

Samples sent to Duke University for genetic testing are de-identified. Genetic information will not be provided to participants. The samples will be coded (with the link kept at the UW) and leftover samples will be disposed at Duke (not returned to the UW).

Potential Benefits of the Proposed Research to the Participants and Others

Although participants may experience a benefit from participating in this study, there is no direct benefit guaranteed to participants. The potential benefits for smokers participating in this study include learning information about their health. As in our past research, we will provide individuals with their test results and other information about their health because it is appropriate clinical practice and helps reduce attrition. Such information will include white cell count, hemoglobin concentration, lipid profile, spirometry results, and results of exercise stress test.

Provisions in Place to Address any Unanticipated Problems or Complications

The study will use the UW-CTRI DSMC chaired by [name], leader of the Cancer Control Program of the UW Comprehensive Cancer Center. [name] is an experienced physician and clinical trial researcher with no involvement in any of this project's research activities. [name] is joined on the DSMC by [name] and [name]. [name] is Associate Professor of Medicine and Medical Director of the HIV/AIDS Comprehensive Care Program at UW Hospital and Clinics who has previously collaborated on clinical trials of smoking cessation with UW-CTRI. [name] is a family physician and otolaryngologist who has served on independent DSMBs for Phase II and III trials at UW-CTRI. Neither has direct involvement with any of the proposed research. The Principal Investigators will report to the DSMC.

This study involves neither medication nor treatment of any sort, therefore the occurrence of any unanticipated health events which are severe, unanticipated, and possibly related to study protocol should be uncommon. Any serious unanticipated health event that study staff become aware of will be queried and reported even if it appears that the serious unanticipated health event is unrelated to study participation. The Principal Investigators will be responsible for the accurate documentation, investigation and follow-up of all study-related unanticipated health events. Unanticipated health event assessment, recording, reporting and investigation will be accomplished through staff training, structured/standardized reports of untoward occurrences/events, and regular monitoring by other study investigators. The DSMC requires that investigators notify NIH and the University of Wisconsin IRB in a timely manner (consistent with IRB and NIH policies) of the occurrence of any SAE or any AE which is severe, unexpected, and possibly related to study protocol. Unanticipated AEs, including less serious problems that merit reporting to the DSMC because they are severe, unexpected, and possibly related to study participation. Any SAE will be queried and reported even if it appears that the serious adverse event is unrelated to study participation. The Principal Investigators will also be responsible for the accurate documentation, investigation and follow-up of all study-related adverse events. Additionally, the IRB will receive an annual report of all serious unanticipated health events and unanticipated health events.

Importance of the Knowledge to be Gained

The results from this research will provide important insight into acute and chronic cardiovascular and pulmonary effects and exposure biomarkers of e-cig use compared to, cigarette smokers and quitters. This information will aid clinicians, scientist, and regulatory bodies to make informed decisions about clinical practice, future research, and public health policy.

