Aim 1. To determine the acute effects of product use on primary cardiovascular (brachial artery flow-mediated dilation, FMD) and pulmonary (spirometry) disease risk biomarkers after an acute product exposure challenge. We will compare acute responses to E-cigs in exclusive E-cig users with responses to cigarettes in exclusive smokers vs. no exposure (never-users). The primary acute exposure biomarkers will be brachial artery FMD for cardiovascular disease (CVD) and FEV1 for pulmonary disease. Secondary measures such as acute changes in HR, HRV, BP, FVC, FeNO, also will be assessed. Acute responses will be related to covariates

such as product use history, self-administration topography, nicotine levels, and other biological risk variables.

Aim 2. To determine relations of chronic product exposure with primary cardiovascular (carotid intima-media thickness, IMT) and pulmonary (spirometry) biomarkers of injury, disease risk, and their mechanisms. We will contrast product use-groups to determine their status on each disease biomarker and within each group, we will relate measures of chronic product exposure to disease biomarkers. The primary exposure biomarker will be carotid IMT for CVD and the primary pulmonary biomarker will be FEV1. Primary analyses will determine the relations of E-cig and cigarette product use groups with each biomarker. In addition, within-group analyses will relate history of prior product use (e.g., duration, patterning, and maximal intensity) with each biomarker. Biomarkers used in secondary analyses will include baseline measures from Aim 1 (such as FMD, HR, HRV, BP, FeNO) as well as carotid echogenicity, PWA, treadmill stress testing parameters, and markers of inflammation and oxidation. Historical and biological covariates (i.e., age, sex, and CVD risk factors) will be used in exploratory moderation and sensitivity analyses to determine the robustness of identified relations. This research will relate acute use of E-cigs and cigarettes with putative cardiovascular and pulmonary disease mechanisms and relate longer term patterns of E-cig and cigarette use with measures of cardiovascular and pulmonary dysfunction and injury.

Aim 3. (Exploratory aim) To examine the relationship between monocyte genomic features and e-cig use status

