We will perform linear regression analyses with genomic features as response and status of e-cig use as predictors. Covariates, such as technical factors, will be included in the model. We will use the FDR q-value method to correct for multiple testing. We will compare e-cig users, smokers and control groups. This will only be done prospectively in 50 e-cig users, 25 matched controls and 25 smokers.

Aim 4 (exploratory hypothesis): Plasma from E-cig and Cigarette users will have higher levels of inflammatory cytokines compared to non-users, and these inflammatory cytokines will activate arterial endothelial cells in an in vitro model.

Recruitment & Study Entry

Participants from the greater Madison, WI area will be recruited via the media recruitment methods (i.e., newspaper, and earned media) that have recruited over 2000 smokers over 2 years. In addition, we will use Internet/Facebook advertisements that have been successful in our recent dual use study (HS-IRB #2012-0844). Interested individuals will be asked to call the study telephone number and leave their name and telephone number for a return and phone screen. Potential participants who pass the phone screen will be invited to attend a study session (Visit 1 Orientation) at the UW Madison University Hospital-Atherosclerosis Imaging Research Program, where they will learn more about the study, have eligibility confirmed, and provide written informed consent. During the phone screen we will collect demographic and contact information (address for mailing reminder appointments and phone number) and document the responses to these screening questions.

If we are not successful in meeting recruiting goals, we will recruit from Milwaukee, WI as we have in numerous previous studies. All research activities will still be performed at UW-CTRI and UW Hospital (CSC).

Inclusion/Exclusion

The eligibility (inclusion) criteria are: ≥ 18 years old, able to read and write English, *no* plans to quit smoking and/or e-cig use in the next month, not using cigars/smokeless/snus tobacco ≥ 1 time/week, having a stable pattern of current product use, and able to walk at least 2 blocks without assistance or stopping. For the different user-groups, participants must meet the criteria listed in Table 1. The exclusion criteria are: current use of a smoking cessation medication, women who are pregnant or plan to get pregnant in the next month, women who might be pregnant, incarcerated individuals.

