Table 1. Use Groups/Eligibility

Group	Cigarette Use	E-cig Use[‡]	CO[†]	Cotinine[‡]
Exclusive smokers	Smokes daily; ≥ 5 cigs/day ^{##} for last 6 mos	<3 uses lifetime	≥ 5	>100
Exclusive E-cig users	≤ 2 days/month for last 6 mos	≥ 5 days/week for last 3 mos	≤ 4	>100
Dual users	≥ 5 cigs/day ^{##} , ≥ 5 days/wk for last 6 mos	≥ 5 days/week for last 3 mos	≥ 5	>100
Never users	<100 cigs/lifetime, none for >5 years	<3 uses lifetime	≤ 4	<100

[‡]Predominant use of a tank system; [†] ≥ 5 ppm indicates smoking; [‡]>100 ng/ml indicates nicotine intake; ^{##}average consumption on smoking days.

Study Design

We will enroll 165 exclusive E-cig users, 165 exclusive cigarette smokers, and 110 former (never-) smokers. We will examine tobacco product use via time-line follow-back use-history measures, real-time measures, and lab measures. Potential participants will be assessed for eligibility via a phone screen. Because biomarker status may be affected by age and sex, we will stratify groups equally for gender (48/52 male/female) and age (≤ 35 / > 35 years).

Screening Call (“Call” - Table 2)

Interested individuals after verbal consent using an approved script, will complete an initial phone screen. Eligible, interested participants will attend an Orientation Visit (visit 1 Baseline)

Visit 1 (“Baseline” - Table 2)

Participants will attend a single or group information session where the study will be explained in detail and they will be given time to read the consent. The participants that still express interest, will be lead to a private room where they can ask any remaining questions, and provide written informed consent. Then they will provide biological samples indexing their tobacco product use (*i.e.*, exhaled CO and urine cotinine) to establish their final eligibility and complete questionnaires that assess cigarette and/or E-cig dependence:

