Power estimates assume $\beta=0.2$, $\alpha=0.05$, and two-tailed tests. Brachial artery FMD is the major CVD index of the acute effects of product use. The single prior small study of product use on acute FMD change showed that amongst 20 smokers, smoking a cigarette produced an FMD response that decreased from 5.6% (SD=5.2%) to 2.8% (SD=3.6) within 30 minutes. The effects of cigarette use were even greater amongst the 20 nonsmokers. We expect that cigarettes will produce a significantly greater impact on FMD than E-cigs; with the pre-post mean values of 6.5% and 3.0% for exclusive cigarette users and 7.5% and 5.5% for exclusive E-cig users (with SD=4.0% for all time points and groups and a conservative pre-post FMD correlation of 0.60). This will yield more than adequate power (>0.80) to detect a Group x Time interaction with $n=165$. We also predict that those using E-cigs and/or cigarettes will show significantly greater challenge-induced reductions in FMD than will never-smokers who use neither product during the challenge (never-smoker means: pre=7.0% and post=7.0%); power will be >0.80 for contrasts of either E-cig or cigarette users with never-smokers ($n=110$). Thus, both products will reduce FMD acutely, but cigarettes will produce a greater decrease. Our experience with health studies with smokers shows that we experience virtually no attrition across samples when two proximal visits are scheduled amongst those who attend an Orientation session. We have modeled power for FMD vs. spirometry outcomes, since our data in hand from the EXHALE and WSHS-2 studies suggest that effect sizes and power will be even greater for the key spirometry indices; so FMD is a conservative test of power.

Potential Risks

The risks associated with this study (breach of confidentiality, brief tobacco withdrawal, blood draw discomfort, stress test effort, and brief discomfort during pulmonary function tests) are minimal compared to the potential benefits to the participants as they gain information on their health that might influence their decisions to quit using these products and compared to the potential benefits that the knowledge gained from this study might have in informing clinical practice and public policy.

Physical Risks

Participants will be allowed to smoke and/or vape their own products ad libitum, following assessment, which will alleviate all withdrawal symptoms. Please refer to the [CLUES Emergency-Safety Procedures MOP](#).

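### Aim 2's primary group contrasts name no covariates: leaving out age and sex costs avoidable precision for carotid IMT (and for FEV1 if in litres), and leaves IMT open to bias if ages differ within the >35 band

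*Combined protocol and SAP*

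**What the plan says.** Under Study Aims, Aim 2, the primary biomarkers are carotid IMT and FEV1, and the primary analysis is a group contrast: "Primary analyses will determine the relations of E-cig and cigarette product use groups with each biomarker". No model and no covariate is named. The next step is also described: "within-group analyses will relate history of prior product use (e.g., duration, patterning, and maximal intensity) with each biomarker". Age and sex come after that: "Historical and biological covariates (i.e., age, sex, and CVD risk factors) will be used in exploratory moderation and sensitivity analyses", with the purpose "to determine the robustness of identified relations".

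The Study Design section treats age and sex as relevant to the outcomes: "Because biomarker status may be affected by age and sex, we will stratify groups equally for gender (48/52 male/female) and age", with age split at 35 years. The upper band is open-ended. The eligibility criteria give only a lower limit (at least "18 years old, able to read and write English").

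The Analysis Plans section does not fill the gap. It holds only power reasoning for acute FMD ("We have modeled power for FMD vs. spirometry outcomes"). The one model with stated covariates is exploratory Aim 3: "Covariates, such as technical factors, will be included in the model". Age and sex are not named there either, so it shows only that the plan can specify covariates, not that it adjusts for age elsewhere.

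The Pulmonary Function Test section cites NHANES-III methods and mentions FEV1 as a percentage, but only for the report to the participant. The scale for analysis is not stated.

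**The concern.** The plan uses age and sex to build the groups and then leaves them out of the primary test. Three consequences follow.

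- **Precision.** When a design balances a factor that predicts the outcome and the analysis ignores it, the outcome variance due to that factor stays in the reported standard error. The test is then conservative and loses power. This needs no imbalance.
- **Bias.** The groups are self-selected. The quota removes the difference between the two age bands but not a difference in age inside a band. If one exists, part of it would appear as a product effect in the primary contrast, with the adjusted result only a robustness check.
- **Duration (secondary).** Among smokers, years of smoking rise with age. The quotas do nothing to separate the two.

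**Working it through.** **The plan's own figure.** The only stated power is for acute FMD (Analysis Plans): above 0.80. The SD of change is 4.0 × √(2 × (1 − 0.60)) = 3.578. The difference in change is 3.5 − 2.0 = 1.5. With 165 per group, 1.5 / (3.578 × √(2/165)) = 3.81, and Φ(3.81 − 1.96) = 0.968. The statement reproduces, but it says nothing about IMT or cross-sectional FEV1.

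**Inputs for Aim 2.** From the documents: group sizes 165, 165 and 110; two-sided alpha 0.05; age bands split at 35. Not in the documents, so assumed: half of each group aged ≤35; ages uniform over 18–35 and over 35 to 50, 60 or 70 (SD of age 9.2, 12.2 or 15.2); age-outcome correlation r of 0.4 to 0.6. The outcome SD cancels and is set to 1.

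**Power, no age gap.** Write k = √(1/n1 + 1/n2) and take the effect 2.80 × √(1 − r²) × k, which has 80% power with age in the model (2.80 = 1.96 + 0.84). For an upper age of 60:

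- Within-band age variance = ½ × 17²/12 + ½ × 25²/12 = 38.1. Total = 38.1 + (21/2)² = 148.4. Within-band share = 0.257.
- Unadjusted, the reported variance is 1 (times k²). The actual variance is (1 − r²) + 0.257r², because the quota already fixes the between-band part. That is 0.881 for r = 0.4 and 0.733 for r = 0.6.
- Unadjusted power, r = 0.4: Φ((2.80 × 0.917 − 1.96)/√0.881) = Φ(0.65) = 0.74. For r = 0.6: Φ((2.80 × 0.80 − 1.96)/√0.733) = Φ(0.33) = 0.63.
- Band indicator only: the reported variance now equals the actual one. Φ(2.566/0.939 − 1.96) = 0.78 for r = 0.4, and Φ(2.24/0.856 − 1.96) = 0.74 for r = 0.6.

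Simulation (upper age 60 or 70; 165 vs 165 and 165 vs 110) agrees:

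| Model | r = 0.4 | r = 0.6 |
|---|---|---|
| Unadjusted | 73–75% | 62–64% |
| Band indicator only | 73–79% over both r | |
| Continuous age | 79–80% | 79–80% |

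At r = 0.1, as might hold for % predicted FEV1, power is about 80% either way.

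**False positives, no true group effect.** A gap of g years in the >35 half shifts the contrast by (r/SD of age) × g/2. For r = 0.6, upper age 60 and g = 5, that is 0.6/12.2 × 2.5 = 0.12 SD. Simulated rates over the assumed ranges, with one group's whole >35 band shifted:

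| Gap in >35 band | Unadjusted, 165 vs 165 | Unadjusted, 165 vs 110 | Band indicator only (both) | Continuous age (both) |
|---|---|---|---|---|
| None | 2–4% | 2–4% | about 5% | 4–6% |
| 2 years | 3–5% | 3–5% | 5–11% | 4–6% |
| 5 years | 7–25% | 6–20% | 9–41% | 4–6% |

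The 5-year case leaves one group with nobody aged 35–40, so it is an upper scenario. If both groups cover the same ages in different mixes, a 2-year gap gives 3–5% and a 4-year gap 6–11%. With an age correlation of 0.05–0.1, a 5-year gap gives about 5–6%.

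**Duration among smokers (n = 165), no true duration effect.** For duration-age correlations of 0.5–0.98 and age-IMT correlations of 0.3–0.6, the unadjusted association is significant in about 50–100% of runs, against about 5% with age in the model. The low end (about 50%) is at correlations of 0.5 and 0.3.

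**The case against.** The authors foresaw the issue. They set quotas on age and sex and planned sensitivity analyses with both, which would reveal a large age-driven difference. If the quotas are met, sex and the between-band age difference are largely handled, and with no gap the unadjusted test errs on the safe side. All of this stands. It does not restore power, because a sensitivity analysis aimed at relations already identified cannot rescue a primary test that missed.

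The power figures are relative. Anchored the other way, at a fixed effect of 0.31 SD and a slope of 0.04 SD per year, 165 vs 165 has 0.83 power unadjusted and 0.91 with continuous age and sex (0.69 and 0.84 for 165 vs 110). A reader might infer that Aim 2 is underpowered. The documents do not support that: they give no Aim 2 effect, SD or power target to fall short of.

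Much of the loss comes from ignoring the quota factor rather than from omitting continuous age, as the band-indicator results show. That also stands, but the indicator alone recovers only part of the power and leaves the within-band bias in place.

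A reader might also infer that the group contrasts are confounded by age. Nothing in the documents shows an age gap inside either band. Nor does the concern carry over automatically to FEV1: as % predicted it would show essentially no power loss and little bias.

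Finally, the duration analysis is additional to the primary contrasts, the same sensitivity sentence can cover it, and periods of quitting weaken the link between duration and age. That widens the range but does not change the direction.

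**Conclusion.** The point holds for carotid IMT, and for FEV1 if it is analysed in litres. As written, the primary test gives up precision that the design has already paid for: roughly 5–7 points of power at an age correlation of 0.4 and 16–18 at 0.6, from about 80%. Bias is a conditional risk, negligible for a 2-year gap within the >35 band and material only for larger ones. For FEV1 as % predicted, what remains is to state the scale. The duration point is secondary: an unadjusted association among smokers could not be told apart from age. How far e-cigarette duration tracks age is unknown, and nothing is claimed for patterning or maximal intensity.

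The gap in the text is certain. Every Aim 2 magnitude rests on the assumed age distributions and correlations. The point should be fixed, but it does not undermine the design.

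**What to change.** - Put continuous age (not only the ≤35/>35 indicator) and sex in the primary Aim 2 model for IMT.
- State the FEV1 scale: NHANES-III % predicted, or litres adjusted for age, sex and height.
- Put age and sex in the within-group duration models.
- Keep CVD risk factors, which may be mediators, in the sensitivity analyses, and report the unadjusted contrasts there too.

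The cost is analysis-plan wording and two or three model degrees of freedom. Age and sex underlie the quotas, and height is measured at Visit 1 (Table 2), so no new data are needed. The duration models pay a real price: for duration-age correlations of 0.75–0.98, the duration standard error becomes about 1.4–5.2 times larger, and a true effect of half the age slope would be detected in only 7–90% of runs. That is the cost of separating duration from age.

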Product use will be related to well-validated biomarkers that sensitively and reproducibly reflect mechanisms, injury, and/or future risk related to cardiovascular or pulmonary disease. Biomarkers will be related to: 1) acute product use in the laboratory (exposure challenges), 2) lifetime history of product use, and/or 3) real-time measures of product use in participants' daily lives. The primary cardiovascular biomarkers are brachial artery flow-mediated dilation (a measure of endothelial function) and carotid intima-media thickness, a measure of subclinical arterial injury and atherosclerosis. The primary pulmonary disease biomarkers will be measures of lung volumes and flow rates (FEV1, FVC, FEV1/FVC, FEF25-75) obtained by spirometry. We also will perform treadmill exercise stress testing (to assess aerobic fitness), electrocardiography (to measure heart rate variability, HRV), and measure heart rate, blood pressure, lipids, HgbA1c, and inflammation/oxidation markers (leukocyte count, C-reactive protein, urinary F2 isoprostanes and exhaled nitric oxide). This research will show how product use-groups differ in response to acute product use and long-term use as they are related to key cardiovascular and pulmonary biomarkers. Objective measures of product use include exhaled CO and plasma nicotine/cotinine and urinary nicotine/cotinine concentrations. We also will determine how history of product use within use-groups is related to biomarker status.

The proposed research will yield vital and comprehensive data regarding product use, subclinical arterial injury, atherosclerosis burden, arterial and pulmonary function, cardiac and aerobic fitness, cardiac autonomic regulation, systemic and pulmonary inflammation, and oxidative stress, as well as other key outcomes. These data will serve as a foundation for future longitudinal investigations of e-cigarette health effects and will inform public policy decisions, clinical intervention, and patient guidance regarding e-cigarettes.

Study Aims

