The CLUES Baseline Questionnaire (appendix) includes segments of several validated surveys to assess cigarette and e-cigarette/Juul dependence motives, tobacco withdrawal, smoking history using time-line follow-back to quantify history of tobacco product use including heaviness of use across time, quit attempts, age of use onset, and exposure to environmental smoke/vapor and symptoms and health effects associated with use. Additionally, they will complete a Medical History Questionnaire (appendix). Participants will bring a list of their medications and cigarettes, E-cigs, and e-juice so we can obtain specific information on product features, including E-cig battery voltage, resistance, flavoring .and nicotine concentration.

Participants will be provided with and trained to use a research smartphone with our previously developed app for EMA tracking of E-cig and cigarette use for 1 week before Visit 2. They will press a button marked “C” every time they start a new cigarette and to press one marked “E” every time they vape (a vaping episode is ≥ 2 puffs on an E-cig that are close together in time). The phone is programmed to prompt them to fill a report every night to gather additional data on recent product use/exposure (*e.g.*, context of use, exposure to others vaping or smoking), symptom reports of common nicotine/smoking/vaping adverse events, and withdrawal symptoms and craving (to determine heavy, dependent use: report duration). The questions from the report widget are in the appendix. Based on previous studies experience, participants will spend <5 minutes/day recording cigarette/E-cig use and answering questions. EMA eliminates the problems of recall bias and prefilling/back-filling of paper-pencil diaries. Smartphones will track data wirelessly in real-time so we can rapidly address assessment non-adherence. Note: For the few participants that do not feel comfortable using a phone we will provide a booklet with the nightly survey to be completed every day for 1 week between V1 and V2. This will be assessed and decided during V1 phone app training.

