To enhance compliance with EMA recording, participants will be paid \$2 for each programmed report ($\approx \$14$ for a 1-week assessment window), and \$36 for returning the smartphone, for a maximum total EMA payment of $\geq \$50$. Over the last 3 days of the EMA reporting period, participants will be sent text messages and an email indicating the time of Visit 2 at CTRI, that they need to bring in relevant smoking or vaping materials to the visit, and that they abstain from food, caffeine and tobacco/nicotine use for 8 hours on the day of the visit. Visit 2 will occur ideally within 2 weeks of Visit 1. In cases where participant become febrile and need to recover from an infection, we will allow up to 1 month between visits to allow them to come back to normal values (CRP levels, glucose levels, urinary Isoprostanes, white cell count and brachial artery reactivity responses). Additionally as a precaution from the current COVID-19 outbreak.

Table 2. Schedule of Events

Visit	Call	V1 BASELINE	V2 CHALLENGE (5-15 days after V1)		
Location	Screening	AIRP	CTRI-pre hut	CTRI-post hut	AIRP
Pre-visit instructions	X	NO need to fast and FREE to smoke	Fasting and NO smoking or vaping for 8 hs		Refrain from smoking after Hut
Partial eligibility questions	X				
Informed consent		X			
Provide CDC and QUITLINE information		X			
Baseline use Questionnaire (QUALTRICS)		X			
Collect medical history (QUALTRICS) and medication list		X			
Obtain height, weight and waist circumference		X			
Collect product use data, photos		X	X		
Urine cotinine (NiCheck1)		X	X		
CO (x1)		X	X ^c	X	
Confirm eligibility, assign arm, confirm V2 date/time/instructions		X			
Provide smart phone + training		X ^b			
Collect phones			X ^b		
Fasting labs (sent to UWHC core lab)			X		
Urinary Isoprostanate/creatinine (CHL)			X		
Pre and post Challenge QUALTRICS survey			X	X	
Vital signs			X ^a		
IMT (M9)			X		
Radial Tonometry (PWA)			X		
Spirometry (x3)			X	X	
FeNO (x1)			X	X	
Plasma Nicotine/cotinine (CHL)			X	X	
BART (M9)			X	X	
HRV and BP			X	X	
Light snack				X	
Resting 12 lead ECG				X ^{e##}	X
ETT					X

^aVital signs will include: heart rate and blood pressure.

^bParticipants will receive the smartphone at visit 1 and return it at Visit 2.

^cCO levels will determine if study should be rescheduled because of recent smoking.

^dCO after challenge is measured after FeNO.

^{e##}single resting ECG done at CTRI instead of AIRP prior to stress testing only in cases that are disqualified for ETT.

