When necessary, V2 visit window could be extended up to one month post V1, in cases of fever or infection where 14 days of recovery might be needed (in addition to safety concerns due to COVID-19 outbreak).

Visit 2: Acute Product Use Challenge Visit (Table 2)

Research smartphones will be collected. Participants will be asked about their food and tobacco product use over the last 8 hours and rescheduled if they are non-abstinent. Fasting urine (for cotinine and F₂ isoprostane/creatinine ratio) and pre- and post-acute challenge plasma nicotine/cotinine concentrations will be collected to be sent to ClevelandHeart labs for analysis and pre-challenge blood samples for fasting complete blood count [CBC], lipid panel, HgbA1c, and CRP are sent to the UW-Core lab for processing.

We will then perform the following tests in this order: spirometry(x3), FeNO(x1), CO (x1), carotid ultrasound, 5-minute rest, radial tonometry for augmentation index, and ultrasound brachial artery reactivity study (simultaneous with HR, HRV, BP), pre-challenge, and collected again post-challenge (except carotid ultrasound) within ~30 minutes. Phlebotomy will be performed from the left arm (contralateral arm used in brachial ultrasound testing) for plasma nicotine and cotinine just prior to the product *challenge* test. Only 100 participants are invited to be part of an epigenetics sub-study (50 E-cig users, 25 smokers and 25 controls), prior to smoking, an additional 16 ml of blood will be collected in Vacutainer CPT™ cell separation tubes for PBMC Isolation containing sodium citrate (Becton Dickinson, Rutherford, NJ). These samples will be pre-processed for monocyte isolation at UW ([name] lab) and frozen and after all 100 participant's samples are collected they will be shipped them in bulk in dry ice for final processing and storage in a liquid nitrogen tank at [name] lab in the Duke Molecular Physiology Institute. These samples will be coded (with the link kept at the UW) and leftover samples will be disposed at Duke. They will not run full genome sequencing, neither will they post this information in a public data repository

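### Table 2 opens Visit 2 on day 5, but the planned 1-week EMA record (7 nightly reports) does not fit before a visit on day 5 or 6

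*Combined protocol and SAP*

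**What the plan says.** All references are to the combined protocol and SAP.

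- **Visit window.** The Table 2 column heading is "V2 CHALLENGE (5-15 days after V1". The other timing statements concern the upper end only: "Visit 2 will occur ideally within 2 weeks of Visit 1" in the Visit 1 section, and, in the note under Table 2, "V2 visit window could be extended up to one month post V1" where fever or infection requires it.
- **EMA period.** The Visit 1 section gives participants a smartphone for "EMA tracking of E-cig and cigarette use for 1 week before Visit 2". On frequency it says "The phone is programmed to prompt them to fill a report every night". Those who prefer paper get a booklet "to be completed every day for 1 week between V1 and V2".
- **Payment.** Each report earns $2, about $14 "for a 1-week assessment window", plus $36 for returning the phone.
- **Start and end of recording.** Footnote b to Table 2 has the phone given out at Visit 1 and returned at Visit 2. The Visit 2 section repeats the collection.
- **Use of the data.** The Study Overview lists "real-time measures of product use" in daily life as one of three things to which biomarkers will be related, joined to the other two by and/or.

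The document sets no 7-day minimum between visits and no minimum number of EMA days, and it gives no rule for a shorter record.

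**The concern.** The phone, the booklet and the payment text all describe one week of recording, and that week has to fit between the two visits. The lower end of the visit window is shorter than a week. Staff can therefore follow Table 2 exactly and still be unable to collect the record that the Visit 1 section specifies.

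What is at stake is the quality of one exposure measure. A participant with fewer recorded days has a less precise estimate of usual use, which weakens any estimated relation between real-time use and a biomarker. Record length would also differ between participants for a scheduling reason, with nothing in the plan on how to handle it.

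**Working it through.** **1. The plan's own figure.** $14 / $2 = 7 reports, and $14 + $36 = $50, the stated EMA total. The planned record is therefore 7 nightly reports.

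**2. Reports possible by visit day.** Let Visit 1 be day 0 and Visit 2 be day d. The phone is held on d evenings if the Visit 1 evening counts, and on d − 1 if it does not. The plan does not say which.

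| Visit 2 on day | Most reports, Visit 1 evening counted | Most reports, not counted | Full 7? |
|---|---|---|---|
| 5 | 5 (5/7 = 71%) | 4 | no / no |
| 6 | 6 (6/7 = 86%) | 5 | no / no |
| 7 | 7 | 6 | yes / no |
| 8 to 15 | 7 | 7 | yes / yes |

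Days 5 and 6 fall short under either count. Day 7 falls short only if the Visit 1 evening is excluded.

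**3. What a shorter record does to precision.** The document gives no variance for daily use, so this step rests on an assumption. Let r be the day-to-day variance divided by the between-person variance, taken as 0.5 to 2, with days independent within a person. The reliability of a k-day mean is 1 / (1 + r/k), and a regression slope on that mean shrinks by this factor.

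| r | 7 days | 5 days | Further slope loss, 1 − (5-day / 7-day) |
|---|---|---|---|
| 0.5 | 1/(1 + 0.5/7) = 0.93 | 1/(1 + 0.5/5) = 0.91 | 2.6% |
| 1 | 1/(1 + 1/7) = 0.875 | 1/(1 + 1/5) = 0.833 | 4.8% |
| 2 | 1/(1 + 2/7) = 0.78 | 1/(1 + 2/5) = 0.71 | 8.2% |

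These losses would apply if every record had 5 days. With only some participants seen early, the study-level loss is smaller. It cannot be computed, because the share seen on day 5 or 6 is not given.

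**4. Weekday and weekend mix.** Suppose weekend use is higher by a fraction u, assumed to be 0.2 to 0.5. Relative to weekday use, the 7-day mean is 1 + 2u/7. A 5-day record with both weekend days has mean 1 + 2u/5. The ratio is 1.08/1.057 = 1.02 for u = 0.2 and 1.20/1.143 = 1.05 for u = 0.5, a shift of +2% to +5%. If both visits fall on weekdays, every 5-day interval (Wednesday to Monday, Thursday to Tuesday, Friday to Wednesday) contains both weekend days, so this is the case that applies.

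**The case against.** The strongest reply is that little turns on this. Both statements can be met for any visit from day 7 or 8 to day 15, which is most of the window. Visit 2 reminders are sent over the last three days of EMA reporting, which suggests that the visit is meant to follow the recording week. EMA is also one source among several. Aim 1 names product use history, topography and nicotine levels as example covariates. The Aim 2 primary analyses compare use-groups, and its within-group analyses use prior history. Neither aim names EMA, the power statement in Analysis Plans rests on FMD, and the 110 never-users have essentially no use to undercount.

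Most of this stands, and it limits the size of the point. It does not remove the mismatch: the reminder timing is not a minimum interval, and Table 2 expressly permits day 5.

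A reader might infer more than the documents support, in four ways:

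- **That early participants supply no usable EMA data.** They supply 4 to 6 nightly reports plus the button presses on those days. Only the full week is lost.
- **That the two statements can never both hold.** They conflict only at the early end of the window.
- **That weekly counts would be up to 29% too low (1 − 5/7).** This presumes that use is analysed as a weekly total. No section defines it so, and payment per report does not define an analysis variable. The Visit 2 section speaks of frequency of use, which can be a rate.
- **That mean daily use could be understated by 5% to 12.5% because no weekend day is recorded.** The arithmetic is 1 − 1/1.057 and 1 − 1/1.143 under the same assumed u. A five-day record without a weekend day runs Monday to Friday and puts Visit 2 on a Saturday, so the figure is conditional on weekend visits. Clinic days are not stated.

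**Conclusion.** The inconsistency is real and minor. The lower limit in Table 2 defeats the 1-week EMA specification for visits on day 5 or 6, and also for day 7 if the Visit 1 evening does not count. Those participants can give 4 to 6 of 7 planned reports, depending on the visit day and the counting rule. That result needs only the document's own figures.

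The cost in precision is modest. The further slope loss of about 3% to 8% for 5-day records rests on the assumed variance ratio of 0.5 to 2 and concerns only participants seen early, whose number is unknown. No primary group comparison, sample size or power figure changes.

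**What to change.** Reconcile the Table 2 lower limit with the EMA text so that the earliest permitted Visit 2 allows seven nightly reports. State whether the Visit 1 evening counts: if it does, the earliest day is 7; if not, it is 8. Leave the upper limit and the one-month extension unchanged.

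For anyone already seen earlier, add one sentence to the analysis plan: EMA use is expressed per recorded day, and the number of recorded days is reported by use-group. Separate weekday and weekend averages are not needed, and they would be undefined for a record with no weekend day.

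The cost is one number in Table 2 and one or two sentences. Two or three early visit days are given up, and the window still runs to day 15.
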